In addition, the exercise level we are using here is exactly the same we used in our previous study (*Mendonca ME, Simis M, Grecco LC, Battistella LR, Baptista AF, Fregni F. Transcranial Direct Current Stimulation Combined with Aerobic Exercise to Optimize Analgesic Responses in Fibromyalgia: A Randomized Placebo-Controlled Clinical Trial. Front Hum Neurosci. 2016 Mar 10;10:68*). We have found this to be an effective and also reasonable level of exercise for FM patients.

Finally all subjects will participate in a 1-week exercise conditioning program according to their randomized group as explained below.

Aerobic Exercise: Each session of moderate intensity AE will last 30 minutes (brisk walking). FM patients will be walking on a treadmill with a workload intensity set to a maximum of 60-70% of age predicted maximal heart rate, following the formula $HR_{max} = 208 - (0.7 * \text{age})$ [36]. Before and after each AE session, there will be warm-up and cool down periods (explained below). During the AE session, the intensity will be modulated based on patient's HR_{max} .

Non-aerobic Exercise: The non-aerobic (nAE) exercise will have a 30 min-duration, but the workload intensity will be set within 5-10% baseline heart rate. We also used this method in our preliminary study [29]. The warm-up and cool down periods will consist of 3-minutes walking on the treadmill at a comfortable self-selected speed.

Conditioning exercise program:

The two groups will participate in a different conditioning exercise program according to their group assignment. Stimulation will only start after the conditioning exercise program.

[figure not shown]
Group of Aerobic exercise: in this group participants will exercise (brisk walking in the treadmill – 60-70% of HRmax) following the schedule below (3 sessions within 1 week):

[figure not shown]
- Week 1: up to 15 min on the Monday (minimum 10 min), up to 25 min on Wednesday and up to 30 min on Friday (days of the week can change to adjust to subject schedule)

If a subject from this group cannot progress beyond 20 min at 60-70% HR max over the initial 1-week period, they will be excluded from further involvement in the study. If they reach 20 min at 60-70% of their HR max, he/she can progress to 30min during the second phase and this will be noted.

Group of Non-aerobic exercise: in this group participants will walk at within 5-10% of their baseline heart rate following the schedule below (3 sessions within 1 week):

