- Week 1: up to 15 min on the Monday (minimum 10 min), up to 25 min on Wednesday and up to 30 min on Friday (days of the week can change to adjust to subject schedule)

Pre-screening and Visit Description

[figure not shown]

Figure 2 - Schematic representation of the intervention. Subjects will be assigned to either: Aerobic or anaerobic exercise (AE or nAE – grey squares) and active or sham transcranial direct current stimulation (tDCS - black squares).

Pre-screening Procedures

During the pre-screening process, the subject will contact a co-investigator usually via a phone call. During this call, the co-investigator will discuss in greater depth the details of the study, explain the study procedures and encourage the subject to ask questions. The co-investigator will ask the subject questions from the phone screening questionnaire, or if the subject desires, this can be arranged to be done in the privacy of the laboratory. We will follow partner's institutional policies regarding communication with study subjects including use of encryption.

Once this information is collected, the co-investigator will consult with the PI regarding the eligibility of the subject, who will then give approval for the subject to come to our laboratory for the screening procedure.

Visit 0 – Consent and Screening Visit

At screening visit the PI and/or a co-investigator will conduct once more a review of inclusion/exclusion criteria to determine the subject's eligibility for enrollment. Study procedures will be reviewed with the subject, and documentation of informed consent will be obtained.

At Screening, the following procedures will be completed:

- Discuss study-specific procedures with the subject
- Obtain a signed and dated consent form
- Review inclusion and exclusion criteria
- Pregnancy test (if applicable)
- Conduct a Demographics Survey, including self-reported hand dominance
- Conduct a Recruitment Survey

Visit 1 – Pre-training walking

If the subject passes the screening for exercise (see section IV) as reviewed by PI, subject will undergo the pre-training walking (30' treadmill at baseline HR). If he/she complete the pre-training walking successfully as described above, then he/she will be randomized during visit 1.1. (subjects will also complete the adverse effects for aerobic exercise questionnaire)

- Pregnancy test (if applicable and wasn't done in visit 0 in the case of eConsent)

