**Visits 0 and 1 may be completed in the same day or broken up into two separate visits as the subject prefers*

Daily pain reports will be collected for the two weeks between V1 and V2.

VISITS 1.1 – 1.3: Subjects will be randomized during visit 1.1. The two groups will participate in a different conditioning exercise program for two weeks according to their group assignment (see section VI). At visits 1.1, we will conduct assessments of pain, quality of life, TPSP, CPM, TMS and EEG acquisition (we will offer the possibility of splitting this visit into two visits if the subject gets too tired). At visit 1.3, we will conduct assessments of pain and quality of life, TPSP and CPM. In all these visits we will conduct AE adverse effects questionnaires.

VISITS 2, 11, 17: assessments of pain (except visit 2), quality of life (except visit 2), TSPS, CPM, TMS and EEG acquisition. At the same visit, tDCS and AE will be performed. Also, tDCS and AE adverse effects questionnaire.

VISITS 6 and 14: tDCS, AE, tDCS and AE adverse effects questionnaire, CPM, TSPS, assessments of Pain

[figure not shown]
VISITS 3, 5, 8, 10: tDCS only and tDCS adverse effect questionnaire. The subjects will have the option of choosing to do the visits remotely home-based tDCS (Soterix Medical 1X1 tDCS mini-CT stimulator device), in order to decrease the burn of daily visits at our site.

[figure not shown]
VISITS: 4, 7, 9, 12, 13, 15, 16: tDCS, AE and tDCS and AE adverse effects questionnaire.

VISIT: 18: Pain and quality of life assessments, TMS, EEG, CPM, TSPS.

[figure not shown]
Replacement of missed sessions (though all the effort will be made to avoid missing sessions) will be allowed to up to 20% of missed sessions (up to 4 total visits) according to the treatment schedule. Follow-up and assessments will be encouraged even if more than 20% of missed sessions given data will be analyzed as ITT (though we expect this to be low). We will allow the following visit windows:

- *between visit 1 and 1.1: 2 weeks*
- *between visits during the conditioning period (from visit 1.1 to 1.3): 2 weekdays*
- *between visit 1.3 and visit 2: up to 1 week*
- *between visit 17 and visit 18: up to 2 weeks (before or after the final follow-up, meaning visit 18 could happen 2.5 months to 3.5 months from visit 17)*
- *between Visit 2 and Visit 17: up to 6 weeks*

[figure not shown]

Detailed Protocol 16

Detailed Protocol 17

VII. DESCRIPTION OF ASSESSMENTS

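### Aerobic-arm patients who fail a treadmill criterion are excluded after randomisation, with no matching rule in the other arms and no stated week-4 follow-up, which conflicts with the planned intention-to-treat analysis

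*Combined protocol and SAP*

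**What the plan says.** All places are in the combined protocol and SAP.

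- **Randomisation.** Under Visits 1.1 – 1.3: "Subjects will be randomized during visit 1.1". Under Visit 1 – Pre-training walking: "If he/she complete the pre-training walking successfully as described above, then he/she will be randomized during visit 1.1". That walk lasts 30 minutes on a "treadmill at baseline HR".
- **Conditioning by arm.** Under Exercise: "all subjects will participate in a 1-week exercise conditioning program according to their randomized group". Under Conditioning exercise program: "Stimulation will only start after the conditioning exercise program".
- **The rule, aerobic group only.** "If a subject from this group cannot progress beyond 20 min at 60-70% HR max over the initial 1-week period, they will be excluded". The sentence goes on to shut these patients out of the rest of the study. The next sentence reads: "If they reach 20 min at 60-70% of their HR max, he/she can progress to 30min during the second phase". The readable text gives no such rule for the non-aerobic group.
- **Length of conditioning.** One week under Exercise, but under Visits 1.1 – 1.3: "The two groups will participate in a different conditioning exercise program for two weeks according to their group assignment".
- **Early outcome data.** CPM and TSPS are measured at visits 1.1 and 1.3.
- **Follow-up.** The paragraph on replacing missed sessions encourages continued assessment because the data will be analysed as ITT. It speaks of missed sessions, not of patients excluded during conditioning.
- **Analysis (section VIII, Planned Analysis).** The primary endpoint is the change in CPM (and TSPS) from baseline to week 4, in a mixed linear model. The set is randomised patients with one or more intervention sessions, and randomisation is placed directly before the first intervention. LOCF (written LOFC) and multiple imputation (MI) are the missing-data methods. Combined versus control is tested first. If it is significant, combined is compared with each single intervention.

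**The concern.** Whether a patient tolerates 60-70% of maximal heart rate is seen only after allocation, and only in the two aerobic arms. The walk before randomisation is at baseline heart rate, so it does not screen for this. Similar patients in the non-aerobic arms stay in. Combined versus control and combined versus tDCS alone then compare a selected arm with an unselected one. Combined versus exercise alone has the rule on both sides.

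Two things are at stake.

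- **Selection.** If excluded patients would have had a different week-4 outcome, the observed arms are no longer comparable.
- **Estimand.** Even with no such difference, excluded patients receive no tDCS. An analysis of those who continued does not estimate the effect in all randomised patients.

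Set membership is also unclear. If conditioning counts as an intervention session, these patients are in the set without a primary endpoint. If only tDCS sessions count, they leave the set after randomisation. The statement that randomisation directly precedes the first intervention fits visit 1.1 only if conditioning counts.

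**Working it through.** **The plan's own figure.** Section VIII gives effect size 0.90, two-sided alpha 0.05, power 85% and dropout 20%. n = 2(1.960 + 1.036)² / 0.90² = 22.2, so 23 per arm; 23 / 0.8 = 28.75, so 29; 4 × 29 = 116. This matches. After 20% dropout, 29 × 0.8 = 23.2 per arm are evaluable and t-test power is 85.0%.

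**Assumptions not in the documents.**
- Fraction excluded p = 5/10/20% of an aerobic arm (about 3 to 12 of 58), on top of the 20% dropout.
- Excluded patients do δ = 1 SD worse at week 4.
- Baseline is visit 1.1. Each early value correlates 0.5 with week 4, and the early values correlate 0.6 with each other. The SD of change is then √(2 − 2 × 0.5) = 1, so SD units are the same for change and for week-4 values.

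**Numbers left if excluded patients are deleted.** 23.2 × (1 − p) = 22.0/20.9/18.6 against 23.2 in control. Power at 0.90 is 84/83/80%. Lost numbers are a minor issue.

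**Selection, no true effect.** With c the share of δ already present at baseline, the bias in the change score is p × δ × (1 − c). Type I error is from simulation of the change score with 20% dropout:

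| c | bias, p = 10% | type I error | bias, p = 20% | type I error |
|---|---|---|---|---|
| 0 | 0.10 SD | about 6% | 0.20 SD | about 9% |
| 0.5 | 0.05 SD | about 5% | 0.10 SD | about 6% |
| 1 | 0 | about 5% | 0 | about 5% |

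A noncentral-t calculation for c = 0 agrees (6.2% and 9.6%). If excluded patients would have done better, the sign reverses.

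**Estimand, no prognostic difference, no effect in excluded patients.**
- All randomised: 0.90 × (1 − p) = 0.855/0.81/0.72 SD at p = 5/10/20%.
- Deletion, or MI assuming missing at random: about 0.90 SD at each p.
- LOCF for excluded patients, other dropouts omitted. Excluded patients contribute a change near zero and have weight p / (p + 0.8(1 − p)) = 0.062/0.122/0.238. The estimate is 0.90 × (1 − weight) = 0.84/0.79/0.69 SD, near the all-randomised value.

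LOCF does not remove selection that the early values do not show: at p = 20% and c = 0, about 0.17 to 0.20 SD of bias remains.

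**The case against.** **Sound exercise level.** The Exercise section says that the level was used in the group's previous study and was reasonable for these patients, and all patients pass risk screening and a 30-minute walk. This stands as a reason not to expect a high exclusion rate. It does not make the rule two-sided.

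**Size.** A reader might infer a false-positive rate near 10%. The documents do not support that. It needs 20% exclusion, a 1 SD difference and no trace of that difference at baseline. The planned endpoint is change from baseline, which cancels a stable difference.

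**LOCF is planned.** It would roughly show the diluted effect if excluded patients gain nothing, so the planned methods are not blind to that case. It is a sensitivity analysis only and leaves hidden selection in place.

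**Dropout.** The 20% allowance may already include conditioning losses, so adding p to it is an assumption. An allowance restores numbers, not comparability.

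**Non-collection is inferred.** A reader might take it as stated that week-4 data are not collected. The text says only that these patients have no further part in the study. No readable passage brings them back, but figures beside the rule and later pages are not shown.

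**The inconsistencies are small.** The two 20-minute sentences conflict only for a patient who reaches exactly 20 minutes. The rule names its own one-week period, and three visits can fit in a week. Reductions on request (Exercise Adverse Effects) can coexist with a capability rule. All this is fair, but these passages decide who leaves a randomised comparison, so they should agree.

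**Conclusion.** The point holds as a conflict between the exclusion rule and the stated intention-to-treat analysis. That the rule exists, applies after randomisation and is written for the aerobic arms only is clear. Its effect on the result is not. With no exclusion rate in the documents, neither size nor direction can be derived, and the figures above are conditional on assumed rates, differences and correlations. Within those assumptions, type I error stays near 5-6% except at 20% exclusion with a large difference that baseline does not show. The estimand problem needs no prognostic difference: when excluded patients benefit less, an analysis of those who continued overstates the all-randomised effect, by up to 0.90 − 0.72 = 0.18 SD at 20% exclusion. This should be fixed. It does not show that the trial's comparisons are invalid.

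**What to change.** 1. In Planned Analysis, define the primary set as all patients randomised at visit 1.1, analysed as randomised, and state that conditioning counts as an intervention session.
2. State that patients who meet the exclusion criterion keep the week-4 CPM/TSPS assessment and visit 18, whatever is decided about study treatment.
3. Report by arm how many met the criterion, including those already excluded. Where week 4 is missing, use visits 1.1 and 1.3 as auxiliary variables in MI. Visit 1.3 is after randomisation, so it should not be a covariate in the primary model. Alongside LOCF, add a delta-adjusted analysis in both directions whose range includes no treatment effect in these patients.
4. Reconcile the two 20-minute sentences and the one-week and two-week descriptions of conditioning, and say how reductions on request relate to the exclusion. No clinical rule is proposed here.

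**Cost.** Wording, and one or two assessment visits for each such patient. Those already excluded can be covered only by the counts and the sensitivity analysis. If followed patients show no effect, power is about 80/75/64% at 5/10/20% exclusion, against 84/83/80% if they are deleted (t-test, 20% dropout). That is the price of the intention-to-treat estimand the plan already states.

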The overall goal of this project is to investigate the mechanisms of optimized tDCS via two important markers of chronic pain, conditioning pain modulation (CPM) and slow temporal summation (STS). In addition, the results of this study will represent a significant step toward developing a novel low-cost therapy for FM and validating a therapeutic novel target.

Sponsors

This study is funded by NIH-NCCIH (1 R01 AT009491-01A1).

II. SPECIFIC AIMS

This trial aims at understanding the mechanisms of optimized tDCS (16 tDCS sessions combined with exercise) on pain control. Optimized tDCS can lead to stronger engagement of the endogenous pain regulatory system that will ultimately lead to increased pain relief in patients with FM. Therefore, we designed a 2x2 factorial mechanistic trial [tDCS (active and sham) and aerobic exercise (active and control)] to test the following aims:

Aim 1 (primary outcome): Evaluate the effects of 4 weeks of tDCS coupled with exercise on the endogenous pain regulatory system assessed by CPM and central sensitization as assessed by TSPS, and compared to either intervention alone and to no intervention. *We hypothesize that tDCS coupled with exercise will result in restoration of pain endogenous regulatory system as indexed by greater decrease in SPS and increase in CPM responses. We also hypothesize to observe differences between groups as exercises may have a larger effect on the insula and somatosensory cortex (which is indexed by SPS) while tDCS seems to have a greater effect on prefrontal and*

cingulate cortex (which is indexed by CPM). Thus, these markers will be important to understand to what extend the nodes of pain matrix may be more involved in pain relief and whether the effects of tDCS and exercises are mainly mediated by an increase in inhibition (increase of CPM) or a decrease of excitation (decrease of TSPS).

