The primary analysis: All the analyses will be performed as intention-to-treat in which all subjects undergoing randomization who receive at least one intervention session (randomization will take place immediately before the first intervention) will be included. We will conduct sensitivity analyses and test different models of handling missing data (LOFC and MI). The change in the primary efficacy endpoint, CPM (and also TSPS), from baseline to week 4 will be tested with a mixed linear model. This model will be adjusted for important demographic variables (i.e., gender) and also baseline clinical parameters where appropriate. All tests will be two-sided (alpha level, 0.05). We will initially test our main hypothesis that the combined treatment induces a greater increase in CPM (and decrease in TSPS) as compared to the control condition. If the effect is significant, we will then test differences between the combined group vs these two interventions alone.

[figure not shown]
In order to understand the time effect of this intervention (using the secondary endpoints added in this model (week1 and follow-up)), we will run a secondary mixed linear model to estimate the rate of change over time by also including an interaction between treatment and time as to detect whether treatment effect changes differently according time. If the interaction is not significant we will then test whether there is a main effect of time that is independent of treatment level (interaction will be then removed from the model). We will adjust this model for important covariates such as age, gender, pain levels (numeric pain scale – NPS), and other baseline clinical outcomes where appropriate. For the secondary clinical variables with a significant effect we will also test whether they moderate the interventions' effects on our mechanistic outcomes, thereby gaining additional mechanistic insights.

To complete our analysis, we will apply a path analysis [1, 2] to the outcome data (CPM and TSPS) to determine if endogenous pain modulation changes (as indexed by CPM and TSPS) associated with the combined intervention (tDCS and AE) is related to direct effects versus indirect effects through improvements in secondary outcomes. We propose that a direct effect of tDCS and AE on the endogenous pain inhibitory system can be inferred if the treatment effect cannot be explained by changes in psychological or functional outcomes.

[figure not shown]

[figure not shown]
Detailed Protocol 23

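### Subjects who stop stimulation have no firm date for the week-4 CPM/TSPS measure or the follow-up, although the ITT analysis includes them

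*Combined protocol and SAP*

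**What the plan says.** Under VIII, Planned Analysis, the primary test is set out as "The change in the primary efficacy endpoint, CPM (and also TSPS), from baseline to week 4 will be tested with a mixed linear model". The analysis set is every randomised subject who receives at least one intervention session. LOCF (printed LOFC) and multiple imputation are named as sensitivity analyses.

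The visit text under Pre-screening and Visit Description ties the measurements to numbered sessions:

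- "VISITS 2, 11, 17: assessments of pain (except visit 2), quality of life (except visit 2), TSPS, CPM, TMS and EEG acquisition", followed by "At the same visit, tDCS and AE will be performed".
- "VISITS 6 and 14: tDCS, AE, tDCS and AE adverse effects questionnaire, CPM, TSPS, assessments of Pain".
- The window for the whole course is "between Visit 2 and Visit 17: up to 6 weeks".
- Visit 18 is placed 2.5 to 3.5 months after visit 17 and has no other anchor.
- Up to 4 missed visits may be replaced. Beyond that, "Follow-up and assessments will be encouraged even if more than 20% of missed sessions given data will be analyzed as ITT".

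Randomisation takes place at visit 1.1, the first of three conditioning visits. The Conditioning exercise program section then takes aerobic-group subjects out of the study altogether if they cannot get past 20 minutes at the target heart rate within the week. It states no matching rule for the non-aerobic group.

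**The concern.** The analysis is indexed by calendar time and the schedule by treatment session. The two agree for a subject who attends everything on time. They separate for a subject who falls behind, and more so for one who stops. An ITT analysis needs an outcome from that subject at the same nominal time as everyone else, and the text does not say when to obtain it.

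Two things are at stake. First, the comparison may drift towards subjects who completed the sessions. The named missing-data methods do not fully repair this. LOCF carries forward a value taken during treatment, and a mixed model or standard imputation fitted mainly to subjects who stayed on treatment will tend to predict stoppers as if they had stayed. Second, the loss need not be balanced. One route out of the trial after randomisation is open to the aerobic arms only, and exercise is one of the two factors under test.

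**Working it through.** **Which visit is week 4?** The visit lists give tDCS at visits 2, 11 and 17 (3 visits), 6 and 14 (2), 3, 5, 8 and 10 (4), and 4, 7, 9, 12, 13, 15 and 16 (7). The sum is 3 + 2 + 4 + 7 = 16, which matches "optimized tDCS (16 tDCS sessions combined with exercise" in Specific Aims. Visit k is thus session k − 1. CPM and TSPS are measured at visits 2, 6, 11, 14 and 17, that is, at sessions 1, 5, 10, 13 and 16, and each of these visits also delivers tDCS and exercise.

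Assume 5, 5, 3 and 3 sessions per week, as the position of the tDCS-only visits (3, 5, 8, 10) suggests. Visits 6, 11, 14 and 17 then close weeks 1, 2, 3 and 4, and visit 17 falls on about day 25. No text equates week 4 with visit 17, but no other visit fits.

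**How far can it move?** Reading the window as the total span from visit 2, the limit is 6 × 7 = 42 days. That is 6 − 4 = 2 weeks past the nominal time. Visit 18 inherits the shift. With 365.25/12/7 = 4.348 weeks per month, 2.5 months is 10.87 weeks and 3.5 months is 15.22 weeks:

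- Visit 17 on day 25 (3.57 weeks): visit 18 falls 14.4 to 18.8 weeks after visit 2.
- Visit 17 at 6 weeks: visit 18 falls 16.9 to 21.2 weeks after visit 2.

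**A subject who stops after session 8 (visit 9).** CPM and TSPS exist from visits 2 and 6. Visits 11, 14 and 17 are all treatment visits the subject no longer attends for treatment. If the subject accepts the encouragement to be assessed, the only limit is 6 weeks from visit 2. If visit 17 does not take place, visit 18 cannot be dated.

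**An aerobic-arm subject who fails conditioning.** This subject is already randomised, has baseline CPM and TSPS from visit 1.1 and has exercised under the assigned programme. If a conditioning session counts as an intervention session, the subject is in the ITT set, yet has no visit 2, 17 or 18.

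**Sample size.** The inputs from Sample Size Calculation are effect size 0.90, alpha 0.05 (two-sided, from Planned Analysis), power 85% and dropout 20%. The normal-approximation formula gives 23 per group. Then 23/(1 − 0.20) = 28.75, rounded up to 29, and 4 × 29 = 116, the stated figure. With 20% lost, 29 × 0.8 = 23.2, so about 23 per arm remain. Power at 23 per arm is 0.86 (normal) or 0.85 (t-test). The planned loss is already paid for.

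**Possible bias (illustration).** Assume that 20% stop, that none of them contributes a week-4 value, that the effect is 0.90 in completers, and that stoppers keep a fraction f of it. The treatment-policy effect is 0.90 × (0.8 + 0.2f):

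| f | Treatment-policy effect | Completer overstatement |
|---|---|---|
| 1 | 0.90 | 0% |
| 0.5 | 0.81 | 0.90/0.81 − 1 = 11% |
| 0 | 0.72 | 0.90/0.72 − 1 = 25% |

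The documents give no value for f.

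**The case against.** The protocol already means to keep these subjects. It continues assessment past the missed-session limit expressly because of ITT, and it expects few subjects to get there. The 6-week limit is counted from visit 2, not from sessions received, so a subject who missed many sessions could still attend visit 17 within a calendar bound. Measuring after a fixed course within a stated window is also defensible in a mechanistic trial. Finally, schedule figures and many later pages are not shown, and week labels or a withdrawal rule may be there.

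Most of this stands, and it limits the point. It does not remove it: an outer bound attached to a treatment visit, with attendance only encouraged, is not a dated week-4 assessment.

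A reader might infer more than the documents support:

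- *That stopping leaves a subject without data by design.* It does not. Assessments are encouraged, and values from visits 6, 11 or 14 may exist.
- *That the trial loses power.* The 29 per arm already includes the 20% allowance.
- *That the 6-week window exists because of missed sessions.* The text does not say so. The link is inferred from the replacement rule nearby, as is any tendency for late measurement to go with poor adherence.
- *That the 20% limit contradicts the cap of 4 visits.* Four of 16 sessions is 25%, but with the three conditioning visits the count is 19, and 20% of 19 is 3.8. The denominator is unstated, so no contradiction is shown.

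**Conclusion.** The concern holds in a limited form and should be acted on. On the readable text, the week-4 endpoint rests on a treatment visit that can come up to 2 weeks late, the follow-up rests on that visit, and subjects who stop have no firm date for either. The aerobic-only removal after randomisation adds a route by which loss can differ between arms.

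The consequence is possible bias and a loosely defined time point. The 0% to 25% range is conditional on 20% stopping with no endpoint data and on a completer-type estimate. Its upper end assumes no effect at all in stoppers, so it should not be read as an expected bias. The verdict also assumes that visit 17 supplies the week-4 value, that the window is the total span from visit 2, that a conditioning session counts as an intervention session, and that the unseen figures contain no dated rule for stoppers.

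**What to change.** In the visit and window text:

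- Replace the encouragement with a scheduled assessment-only visit 17 (CPM, TSPS, pain, quality of life; no stimulation or treadmill). It applies to every randomised subject who stops treatment and has not withdrawn consent to assessment.
- Date it 4 weeks from visit 2, or from the planned visit 2 date if stimulation never started, and keep it within the existing 6-week limit.
- Count visit 18 from that date.
- State that visit 17 supplies the week-4 value in the model, and record days since visit 2 for all subjects so that the remaining spread in timing can be examined.

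Reconcile the conditioning rule with the visit text and the ITT definition, so that leaving treatment does not also remove a randomised subject from assessment. The clinical rule for leaving treatment is not in question here.

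The cost is a short amendment. The assessments and visit slots are already planned, and the sample size stays at 116. Some subjects who stop would attend one visit without treatment. The protocol is dated March 2023 and refers to recruitment in 2020 and 2021, so an amendment reaches only subjects still in the trial. Subjects lost to contact or who withdraw consent would still be missing.
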